	
week 24 and week 52 visits. Screening visit value will be used as reference value for comparison with further values.
 

Check contraindications, warnings and precautions to injection Contraindications, warnings and precautions to injection must be checked at the beginning of the First Injection Visit.

Urine Pregnancy Test/Birth Control Women of child-bearing age will be asked to perform a urine pregnancy test before the Injection Visits. The result of the urine pregnancy test must be negative in order to proceed with vaccine administration. In addition, participants who are able to become pregnant or could impregnate a partner are required to have used approved contraception for least 30 days prior to the study vaccination, and commit to use it for 90 days after the study vaccination.

Screening conclusion Participants will be deemed eligible to participate upon reviewing medical history and inclusion and exclusion criteria. This will occur prior to vaccination on First Injection Visit and will be verified before Second Injection.

Assess pre-injection vital signs (body temperature, blood pressure, pulse rate and respiratory rate) The body temperature of all participants needs to be measured prior to any study product administration on First and Second Injection Visits. Body temperature may be measured by any method (oral, axillary). If the participant has fever (fever is defined as temperature <math>\geq 38.0^{\circ}\text{C}</math> orally or <math>\geq 37.8^{\circ}\text{C}</math> axillary) on the day of injection, the injection will be rescheduled within 1 week.

Check and record prior medications and concomitant medication/injection Prior medications and concomitant medication/injection must be checked and recorded in the eCRF. Prior medications should include any medication taken by the participant within 14 days prior to screening. Participants will be asked to avoid over-the-counter medications such as antipyretics (e.g., acetaminophen) and anti-inflammatory medications (e.g., ibuprofen, naproxen) in the 12 hours before study vaccine receipt but will be allowed to take these over-the-counter medications as needed to treat fever or other AE after vaccination. Usage of these over-the-counter medications will be recorded as concomitant medications and linked to the AE collected as solicited or unsolicited events, as the case may be.

Check and record intercurrent medical conditions Any medical conditions should be collected in the clinical chart and recorded in the eCRF.

Baseline serology Approximately 25 mL of whole blood will be collected from each participant at First Injection Visit, Day 28, Day 84, week 24 and week 52 and separated for serum. The serum will be aliquoted. The results of antibody testing from baseline serum will not be used to determine eligibility for enrolment; instead, results will solely be used for analysis and comparison purposes. Presence of pre-existing SARS-CoV-2 antibodies found in baseline serum will be used for a stratified immunogenicity and efficacy sub-analysis. The second aliquot will be

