--	--

	
stored as a back-up. For participants who entered in the blinded version and then were unblinded and vaccinated, baseline serology will not be performed again, taking the values from the baseline visit performed at the first visit.
 

• For linking purposes, each participant will be assigned a treatment identification number. The number of each administered treatments must be recorded in the eCRF.

• Injection of study vaccine After completing all prerequisite procedures prior to injection, one dose of the assigned vaccine will be administered IM in the deltoid muscle, preferable of the non-dominant arm. If the investigator or delegate determines that the participant's health on the day of administration temporarily precludes administration, the visit will be rescheduled within 1 week. There will be a 15-minute wait after each vaccination to monitor for any rare anaphylactic reaction. At Day 56 after first vaccination, all participants will get a second injection of the investigational vaccine (Second Injection Visit)

• Safety participant contacts Every 4 Weeks for 52 weeks there will be telephone calls following vaccination. They will be used to continuously collect any SAE and MAE data. Participants can report any AE they experience at any time during the study period; however, only SAE and MAE will be entered into the eCRF. In-person visits will occur for Day 28 visit (to collect solicited and unsolicited events, Day 56 (Second Injection Visit), Day 84 and Week 24, and Week 52 visits.

• Efficacy participant contacts All participants will have efficacy participant contacts weekly, for 52 weeks following vaccination. There will be approximately 52 efficacy participant contacts. All efficacy participant contacts will be emails, although other methods such as phone calls or text messages, if preferred, are acceptable. Each participant contact needs to be recorded in the study electronic case report form. The purpose of these participant contacts is to ask if the participants had any symptoms of illness they may be experiencing, regardless of severity. Any possible COVID-19 relevant symptoms will trigger laboratory testing for SARS-CoV-2 infection.

• Illness participant contact visits (Confirmed or suspected infection during study) Participants will be provided detailed instructions regarding the signs and symptoms of COVID-19 disease at each participant contact and will be instructed to seek medical attention and notify study staff should symptoms occur. Symptoms of interest include fever, cough, difficulty breathing, diarrhea, nausea, vomiting, prolonged fatigue, respiratory symptoms, chills, myalgia, sore throat, headache, congested/runny nose, pneumonia, difficulty swallowing, anosmia/ageusia (loss of sense of smell/taste), and neurological events. During the observation period of the study, if any of these symptoms develop in a participant, he/she should immediately follow local procedures for care of suspected COVID-19 illness and contact the study team. If a COVID-19 infection is found during the study, a case investigation will be undertaken according to locally recommended procedures.

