--	---

- If COVID-19 is suspected, the participant will have a nasopharyngeal/throat swab taken. Testing for COVID-19 by PCR will be performed at the local clinical laboratory.
- If negative, the test will be repeated in 3 days from the first testing day.
- All attempts will be made to re-test positive samples in a reference laboratory. If the local lab is also a reference laboratory, then a confirmatory sample is not required.
- If the PCR is positive, nasopharyngeal/throat swabs will be taken every 2 days times 3 and then weekly and tested for COVID-19 by PCR until a negative sample is obtained.
- A serum sample (10mL blood) will be collected at the time of illness presentation and testing for SARS-CoV-2 anti-N IgG antibodies will be performed at Nexelis Laboratories (Canada).
- At Day 21-28 post-illness, a second serum sample will be taken and sent to the central laboratory for anti-N IgG.
- Participants who were PCR negative will also have that visit on day 21-28, where they will be tested for SARS-CoV-2 antibodies (Nexelis Laboratories (Canada)). This visit takes place at the research site where the participant is enrolled.
- Participants who develop COVID-19 infection post-vaccination will be carefully monitored for vaccine-related disease enhancement in collaboration with their primary physician who will be encouraged to obtain specimens in accordance with the Brighton Collaboration definition (Munoz, 2020), including a serum sample tested locally for C-reactive protein (CRP), ferritin, and procalcitonin, biomarkers that have been associated with predicting more severe disease outcome in infected patients.

Participants who develop COVID-19 disease will continue to be followed for other study outcomes by telephone while in isolation, and at the study site once recovered and released from isolation by public health officials.

- **Final serology**

Approximately 25mL of whole blood will be collected and will then be separated into serum at week 52. The serum will be aliquoted. The first aliquot will measure anti-N IgG antibodies, at the Nexelis Laboratories (Canada). The second aliquot will be stored as a back-up. The one-year antibody levels measured against anti-N IgG antibodies will be compared to the participant's baseline levels to evaluate the exploratory efficacy analysis against asymptomatic infection.

- **E-diary and Diary Cards**

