#### 3.2 Study Groups

A total of 500 participants will be enrolled to receive the vaccine. All participants will be monitored for solicited adverse events for 7 days, unsolicited adverse events for 28 days, SAEs and MAEs for the one year duration of the study, and antibody measurements at baseline, Day 28, Day 84, week 24, and week 52. A subset of 50 participants will have cellular immunity measured at those same intervals.

This protocol amendment provides for unblinding of participants who were entered into the study in the double-blind schedule. For participants who entered the double-blind schedule, the visit process will be as follows:

a) Sites will receive an unblinding list detailing participants who received placebo or study vaccine. Participants who received placebo will be invited to continue in the study under the

open-label study scheme and should make visits from V1.B (first vaccine) onwards, after signing the informed consent, completing visits on day 28 (V2.B), day 56 (second dose) (V3.B), day 84 (V4.B), week 24 (V5.B) and week 52 (V6.B). In this group of participants already enrolled, no antibody dosage collection will be performed at the V1B visit; the V1 values at study entry will be taken. The letter B is added to the visits to differentiate this group of participants who must reorganize the schedule of visits from the administration of the first dose of CoVID vaccine after the unblinding. The procedures for this group are detailed in Table 2.

b) Participants who, after the unblinding, are found to have received study vaccine at the initial visit, will complete the visits established by protocol together with the administration of dose 2 of the study (day 56) onwards, after signing the informed consent. In this group of participants there will be no changes in the nomenclature of the visits.

For both arms (placebo and study vaccine), efficacy contacts are restarted with the second injection visit.

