### 3.4 Procedures

Table 1. In-Person Visits

Intervention		Visit 1	Visit 2	Visit 3	Visit 4	Visit 5	Visit 6
		Day 0 (Screening and First Injection Visit)	Day 28	Day 56 (Second Injection Visit)	Day 84	Week 24	Week 52
Visit window			+/- 7 days	+/- 7 days	+/- 7 days	+/- 14 days	+/- 14 days
Informed Consent		•					
Review Consent		•	•	•	•	•	•
Collect Demographic and Participant Contact Information		•					
Blood sample collected for HIV viral load and CD4/CD8 counts		•				•	•
Urine Pregnancy test- women of childbearing potential		•		•			
Review Inclusion and Exclusion criteria		•		•			

Medical History	●		●				
Check and record prior concomitant medication and vaccines	●		●				
Check and record intercurrent medical conditions	●		●				
Check Contraindications to vaccine	●		●				
Pre-injection vital signs	●		●				
Study group and treatment number allocation	●						
Screening conclusion	●						
Administration of Study Product	●		●				
Safety participant contact (Phone call or in-person visit)			Every 4 weeks (Day 28, 56 and 84 is in person)				
Efficacy participant contact (message) (a)			Weekly from Day 7- week 52 (visit window: +3 days)				
Safety participant contact: in-person visit	●	●	●	●	●	●	●
Paper diary provided to participant	●		●				
E-diary or diary card reviewed with participant and data collected and uploaded to eCRF		●					
Immunogenicity participant contact: in-person visit	●	●	●		●	●	
Blood Sample Collected for ELISA and neutralizing Antibody testing (~25mL)	●	●		●	●	●	
Blood Sample Collection for ICS testing (~30mL) (b)	●	●		●	●	●	
Study conclusion							●

● is used to indicate a study procedure.

(a): If it is preferable, a phone-call or text instead of email for an efficient participant contact is acceptable

(b): In the subset of approximately 50 participants who will have cellular immunity measured

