**Detailed description of study procedures and interventions is outlined in Section 5.1**

**Table 2. Procedures for the group of participants assigned to placebo arm. In-person visit**

	Visit 1.B	Visit 2.B	Visit 3.B	Visit 4.B	Visit 5.B	Visit 6.B
Intervention	Day 0 (First Injection)	Day 28	Day 56 (Seco nd Inject ion)	Day 84	Week 24	Week 52
Visit window		+/- 7 days	+/- 7 days	+/- 7 days	+/-14 days	+/-14 days
Informed Consent						
Review Consent		•	•	•	•	•
Collect Demographic and Participant Contact Information						
Blood sample collected for HIV viral load and CD4/CD8 counts					•	•
Urine Pregnancy test- women of childbearing potential	•		•			
Review Inclusion and Exclusion criteria [2]			•			
Medical History	•		•			
Check and record prior concomitant medication and vaccines	•		•			
Check and record intercurrent medical conditions	•		•			
Check Contraindications to vaccine	•		•			

Pre-injection vital signs	●		●					
Study group and treatment number allocation								
Screening conclusion								
Administration of Study Product	●		●					
Safety participant contact (Phone call or in-person visit)				Every 4 weeks (Day 28, 56 and 84 is in person)				
Efficacy participant contact (message) (a)				Weekly from Day 7- week 52 (visit window: +3 days)				
Safety participant contact: in-person visit	●	●	●	●	●	●	●	
Paper diary card or e-diary provided to participant	●		●					
E-diary or diary card reviewed with participant and data collected and uploaded to eCRF		●		●				
Immunogenicity participant contact: in-person visit		●	●		●		●	
Blood Sample Collected for ELISA and neutralizing Antibody testing (~25mL)		●		●	●		●	
Blood Sample Collection for ICS testing (~30mL) (b)		●		●	●		●	
Study conclusion							●	

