Approximately 25 mL of whole blood will be collected from each participant at First Injection Visit and separated for serum. The serum will be aliquoted. The first aliquot will be used to measure for baseline antibodies against SARS-CoV-2. Presence of pre-existing SARS-CoV-2 antibodies found in baseline serum will be used for a stratified immunogenicity and efficacy sub-analysis. The second aliquot will be stored as a back-up. In participants who entered in the blind version and then were unblinded and vaccinated, baseline serology will not be performed again, taking the values of the baseline visit performed in the first visit.

- **Blood collection for ELISpot and ICS measurement**

In a subset of approximately 50 participants, approximately 30mL of whole blood will be collected from participants, in addition to the 25mL being collected for ELISA antibody analysis. TNF, IL-4, IL-5, IL-13 will be measured by ICS on first-injection day, Day 28, Day 84 and Weeks 24 and 52 after vaccination. PBMC will be shipped on dry ice to Nexelis Laboratories (Canada).

- **Check contraindications, warnings and precautions to injection**

Contraindications, warnings and precautions to injection must be checked at the beginning of each Injection Visit.

- **Urine Pregnancy Test/Birth Control**

Women of child-bearing age will be asked to perform a urine pregnancy test before each Injection Visit. The result of the urine pregnancy test must be negative in order to proceed with vaccine administration. In addition, participants who are able to become pregnant or could impregnate a partner are required to have used approved contraception least 30 days prior to the study vaccination and for 90 days after the study vaccination.

- **Assess pre-injection vital signs (body temperature, blood pressure, pulse rate and respiratory rate)**

Body temperature of all participants needs to be measured prior to any study product administration. Body temperature may be measured by any method (oral, axillary). If the

participant has fever (fever is defined as temperature  $\geq 38.0^{\circ}\text{ C}$  orally or  $\geq 37.8^{\circ}\text{ axillary}$ ) on the day of injections, the injection visit will be rescheduled within 1 week.

- **Screening conclusion**

Participants will be deemed eligible to participate upon reviewing medical history and inclusion and exclusion criteria. This will occur prior to vaccination at First and Second Injection Visit.

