## **12.2 Endpoint Review Committee**

The Endpoint Review Committee (ERC) will be blinded to the treatment assignments. Each endpoint case will be reviewed independently by two ERC members to confirm endpoint and severity; if their adjudications conflict, the endpoint will also be reviewed by a third member and the endpoint will be adjudicated by the majority vote. Members of the ERC will be appointed by the Study Steering Committee. Each positive laboratory result will be reviewed by the ERC. A detailed outline of ERC regulations and endpoint case criteria, in addition to the criteria defined below, will be available in the ERC charter.

Endpoints cases are defined by any of the following events:

1. A participant has an illness visit and virological confirmation (positive PCR test). PCR SARS-CoV-2 tests are permitted to be carried out at local study sites. Every effort will be made to verify positive PCR tests in a central reference laboratory.
2. A participant has an illness visit and serological confirmation of SARS-CoV-2. A positive serology test is defined by a four-fold rise or greater to N antibody titers in association with the illness.
3. A participant has illness visit and both virological and serological confirmation.
4. A participant who does not present with any symptoms (does not have any illness visits) but demonstrates seroconversion to the N antigen between the Injection and Week 52 visits.

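### Former placebo recipients have no blood sample at their first Ad5-nCoV dose, so their baseline predates vaccination by an unlimited placebo interval

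*Protocol*

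**What the plan says.** Section 1.3 states that the trial began double-blind against placebo at 2:1. Under section 3.2, participants found to have received placebo re-enter at V1.B, which is their first active dose, and then follow Day 28, Day 56, Day 84, Week 24 and Week 52 visits counted from there. For them, "no antibody dosage collection will be performed at the V1B visit; the V1 values at study entry will be taken".

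The synopsis says the same under Baseline serology: "For participants who entered in the blinded version and then were unblinded and vaccinated, baseline serology will not be performed again". Section 5.1 agrees: "baseline serology will not be performed again, taking the values of the baseline visit performed in the first visit".

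Section 3.2 names Table 2 as the schedule for this group. Its antibody and ICS rows are blank at V1.B, and so is the row "Blood sample collected for HIV viral load and CD4/CD8 counts". Table 1 marks all three at Visit 1 for everyone else. The synopsis and section 5.1 make the screening value the reference for later viral load, CD4 and CD8 results.

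Baseline is then used in several places. The synopsis and section 5.1 state: "Presence of pre-existing SARS-CoV-2 antibodies found in baseline serum will be used for a stratified immunogenicity and efficacy sub-analysis". The synopsis also says: "The one-year antibody levels measured against anti-N IgG antibodies will be compared to the participant's baseline levels". Section 12.2 counts as an endpoint case a symptom-free participant who "demonstrates seroconversion to the N antigen between the Injection and Week 52 visits". Section 9.3.3 uses the CD4 fall of at least 20% and the CD4/CD8 change from baseline. Section 9.3.4 uses GMI and seroconversion.

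**The concern.** The endpoints are timed from vaccination. For former placebo recipients the vaccination clock starts at V1.B, while the reference sample dates from V1, before the placebo interval. The protocol sets no limit on that interval, does not call for a later blinded-phase sample, and does not separate the group in the analysis.

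Two distinct effects follow.

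1. **Undetected SARS-CoV-2 infection between V1 and V1.B.** The resulting titre rise is counted as vaccine response in GMI and, on the usual fold-rise reading, in seroconversion (the protocol does not define that term). The person is classed as seronegative at baseline. The anti-N conversion is dated after the injection although the infection came before it.
2. **CD4 and CD4/CD8 change.** With or without infection, the change covers unvaccinated as well as vaccinated time. Section 9.1 gives the effect of vaccination on the course of HIV disease as the purpose of the study, so the two should not be mixed in one group only.

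**Working it through.** No figure in the protocol bears on this point; section 9.1 says that the sample size has no statistical basis. The check therefore compares the schedules and then works through assumed ranges.

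**Pre-dose samples at the first Ad5-nCoV dose**

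| Sample | Table 1, Visit 1 | Table 2, Visit 1.B |
|---|---|---|
| ELISA/neutralizing antibody | marked | blank; next at V2.B |
| ICS (subset) | marked | blank; next at V2.B |
| Viral load, CD4/CD8 | marked | blank; next at Week 24 |

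**Inputs**
- From the protocol: placebo share 1/3 (2:1, section 1.3); total 500; Day 28 response at the same dose in healthy adults of 47% neutralizing and 97% RBD ELISA (section 1.2).
- Assumed, because the protocol does not give them: 60 to 300 blinded enrollees; undetected infection f = 5% to 20%; titre rise from infection k = 10- to 20-fold; V1 to V1.B gap g = 4 to 26 weeks.

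**People affected**
- Former placebo recipients n = 60/3 to 300/3 = 20 to 100, a share w = n/500 = 0.04 to 0.20.
- Infected undetected n × f = 20 × 0.05 to 100 × 0.20 = 1 to 20. These are also the anti-N conversions that could be misdated.

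**Excess seroconversion**, if every infected person counts as seroconverted: f(1 − p) in the subgroup, w × f(1 − p) pooled.
- Neutralizing, p = 0.47: 0.05 × 0.53 = 2.65 points to 0.20 × 0.53 = 10.6 points; pooled 0.04 × 2.65 = 0.11 to 0.20 × 10.6 = 2.12 points.
- S-RBD, p = 0.97: 0.05 × 0.03 = 0.15 to 0.20 × 0.03 = 0.60 points; pooled 0.006 to 0.12 points.

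**GMI on the V1 baseline divided by GMI on a V1.B baseline**, for the same post-dose titres: k^f in the subgroup, k^(w × f) pooled.
- Subgroup: 10^0.05 = 1.12 to 20^0.20 = 1.82.
- Pooled: 10^0.002 = 1.005 to 20^0.04 = 1.13.
- Widening k to 4- to 100-fold gives 4^0.05 = 1.07 to 100^0.20 = 2.51 in the subgroup.

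**Unvaccinated share of the CD4 interval**
- Week 24, g/(24 + g): 4/28 = 14% to 26/50 = 52%.
- Week 52, g/(52 + g): 4/56 = 7% to 26/78 = 33%.

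The number of additional or missed 20% CD4 falls cannot be derived from the protocol.

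**The case against.** The written exception covers antibodies only. Section 3.3 describes a pre-vaccination draw for viral load and CD4 at the first injection visit for all participants, and the synopsis places the ICS baseline immediately before vaccination. On that reading the blank cells in Table 2 are an inconsistency rather than a decision. However, section 3.2 points to Table 2 for this group's procedures, and a site following it draws nothing at V1.B. The general text shows the standard from which this group departs.

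The sizes rest wholly on assumptions. Weekly contacts, a broad symptom list, repeat PCR and paired anti-N sera would catch most symptomatic infections that are reported. Known infection can be recorded at V1.B and handled in the according-to-protocol cohort (section 6.2). This stands, and it limits the first effect to infections that were asymptomatic or not reported.

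The pooled effects are small. The largest neutralizing shift, 2.1 points, is less than half the 95% half-width at n = 500 and p = 0.47, which is 1.96 × √(0.47 × 0.53/500) = 4.4 points. This also stands. So do four narrower points:
- The anti-N output is a descriptive listing reviewed by the Endpoint Review Committee.
- ICS is analysed as positive rate and level, so the missing sample harms no change-from-baseline endpoint.
- The primary viral load endpoint is detectability, not change.
- Without a control group, a V1.B sample would align the CD4 interval but would not isolate a vaccine effect.

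Finally, a with/without analysis could be left to the SAP. The sampling schedule could not: no analysis can recreate a titre or CD4 count that was never drawn.

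**Conclusion.** The point holds. Antibody carry-forward is explicit in three places. For CD4/CD8 it follows from the blank V1.B cell together with the screening-reference rule.

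The damage is concentrated in the former placebo subgroup and in secondary and exploratory outputs. Under the assumed ranges, the subgroup's neutralizing seroconversion rises by 2.7 to 10.6 points and its GMI is 1.12 to 1.82 times what a V1.B baseline would give. The GMI ratio compares two baseline definitions and is not bias against a known truth. For CD4, 14% to 52% of the interval behind the Week 24 change is unvaccinated time; that describes the interval and is not an effect size.

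The effect on pooled primary S-RBD seroconversion is probably negligible. The 47% and 97% rates come from healthy adults; lower rates in people with HIV would leave more room for excess. The defect should be corrected because the remedy is cheap, but it does not undermine the trial's main result.

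**What to change.** Define baseline as the last sample before the first Ad5-nCoV dose, and amend the synopsis, sections 3.2 and 5.1 and Table 2 to agree. Add to Table 2 at V1.B the standard pre-dose serum draw and the viral load/CD4/CD8 tube, with ICS in the subset.

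Where V1.B has already passed:
- Use any stored serum taken before the first Ad5-nCoV dose.
- Otherwise test anti-N on V2.B serum against V1. The vaccine expresses only the S protein and back-up aliquots are kept, so an anti-N rise flags infection acquired before or around the first dose. Do not date those conversions as post-vaccination. The V2.B window of 28 ± 7 days narrows the uncertainty after the dose to 21 to 35 days, but this does not restore a pre-dose titre or CD4 count.
- Report GMI, seroconversion, the serostatus strata, and CD4 and CD4/CD8 change with and without former placebo recipients who have only a V1 baseline.

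The cost is one routine draw and its assays at an existing in-person visit, for about one third of blinded-phase enrollees. If that visit has passed, it is anti-N testing on serum already collected, a dating rule and one additional analysis.
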